## Outcomes:

**Primary outcome:** The primary endpoint (the failure event) of this study is the time to return of disease activity after the third month post-first-infusion, objectively demonstrated by development of new T2 hyperintense lesions or Gd-enhancing lesions on the MRI or a clinical relapse. A relapse is defined as new or worsening neurologic symptom(s) with an objective change on the EDSS of at least 1.5 points for participants with baseline EDSS scores of 0 or 0.5 and at least 1-point change for participants with EDSS of 1 or more, as determined by the *examining neurologist*. Symptoms must have been attributable to MS, last  $\geq 48$  hours, been present at normal body temperature, and preceded by at least 30 days of clinical stability. If a new or worsening neurological symptom did not fulfil the above-mentioned criteria, but was associated with a corresponding new or enhancing lesion on the MRI that is done in 30 days after the start of that symptom, it is still considered a clinical relapse.

### Secondary outcome:

**Disability:** six-month confirmed worsening or improvement of disability: We will report the proportion of patients who experience one step worsening or improvement of EDSS that is confirmed on a clinical visit six months later.

**Quality of life measures:** We will administer Neuro-QoL in the computer-adaptive test (CAT) format before the infusions and in all the subsequent clinic visits.

**Assessment of T and B-cell phenotypes and function at baseline and 18-24 months post-B-cell depletion**

The assessment T and B-cell phenotypes and function and analysis of the central and peripheral B-cell tolerance checkpoints, as well as measurement of cytokines will be done at Yale University. 30 milliliters of blood will be drawn from the participants before start of the treatment with ocrelizumab (at the screening visit) and 12 or 18 months after the second course of ocrelizumab infusion (month 18 or 24 of the study) and will be sent to Yale University for the analyses explained below.

We will investigate the T and B-cell phenotypes in the blood samples from the participants in the study, pre-treatment and after they repopulate their peripheral B-cells likely at either 18- or 24-months time points. We will follow the frequencies of  $CD3^+CD4^+CD25^{hi}CD127^{lo}FOXP3^+$  Tregs, circulating  $CD3^+CD4^+CXCR5^+PD-1^+$  Tfh cells increased in several autoimmune diseases, and other CD4+ and CD8+ naïve and memory T cell subpopulations. We will also assess the production of several cytokines including IL-2, IL-4, IL-6, IL\_10, IL-17, IL-21, IFN-gamma and TNF-alpha by Tregs and other T cell subsets after activating PBMCs with phorbol-12-myristate-13-acetate (PMA) and ionomycin for 4 hours in the presence of GolgiStop (BD Biosciences) and intracellular staining with specific monoclonal anti-cytokine antibodies as previously reported by our laboratory. Hence, we will determine if the abnormal production of IL-17 and IFN-gamma previously identified in Tregs from people with MS or their elevated Tfh frequencies are corrected after two courses of anti-B-cell deletion. In addition, we will assess *in vitro* the suppressive function of Tregs from people with MS before and after B-cell deletion. Indeed, Tregs from people with MS have been reported to display decreased suppressive function and we will therefore be able to determine if ocrelizumab can normalize Treg function and if this feature is associated with long-term disease suppression.

We will also characterize various B-cell subpopulations in the blood of people with MS before and after treatment with ocrelizumab. We will follow the frequencies of  $CD19^+CD10^+CD27^+IgM^{hi}CD21^{lo}$  transitional B-cells that recently emigrated from the bone marrow,  $CD19^+CD10^-CD27^+IgM^+CD21^+$  mature naïve B-cells,  $CD19^+CD10^-CD27^+IgM^+CD21^+$  circulating marginal zone/ IgM memory B-cells,  $CD19^+CD10^-CD27^+IgM^-IgG^+CD21^+$  and  $CD19^+CD10^-CD27^+IgM^+IgA^+CD21^+$  conventional IgG+ and IgA+ isotype switched B-cells as well as unconventional  $CD19^+CD10^-CD27^+CD21^{lo}CD11c^+$  memory B-cells that express T-bet, contain autoreactive clones and are generated after TLR activation in the presence of IFN-gamma and IL-21. The impact of anti-B-cell therapy on B-cell activation will also be determined by following CD69 expression that we previously reported to be increased on B-cells from people with MS. The expression of other B-cell activation markers such as CD80, CD86, TACI and FAS will also be assessed by flow cytometry on each

Version: 2.0

Date: 3/8/2019

B-cell subsets described above. We will also obtain a preview on the peripheral B-cell selection in MS by characterizing their proliferative homeostasis history by following the expression of proliferation marker Ki67 and using the detection of Kappa recombination excision circles (KREC) by quantitative PCR in freshly isolated B-cell subpopulations from healthy controls and people with MS before and after anti-B-cell deletion as previously described. Indeed, we previously reported that mature naïve B-cells from people with MS have undergone increased homeostatic expansion in the periphery that may result from the amplification of autoreactive clones. Altogether, these studies will determine the impact of anti-B-cell therapy on the phenotype and function of T and B-cells in people with MS.

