#### Inclusion criteria:

- Age 18 years and older.
- Diagnosis of RRMS based on revised McDonald criteria
- At least two Gd-enhancing lesions on the brain or spinal cord MRI done in the prior three months
- Naïve to disease modifying therapies or using an injectable therapy (interferons or glatiramer acetate); or, if history of receiving natalizumab, fingolimod, dimethyl fumarate and teriflunomide, no exposure for past three months
- Expanded Disability Status Scale (EDSS) score at the time of screening = <3

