#### Exclusion criteria:

- Contraindication to treatment with anti-CD20 antibodies, including being seropositive for HBsAg or HIV antibody or T-spot (or Quantiferon-Gold) positive
- Ever received B-cell depleting antibodies (rituximab, ocrelizumab, ofatumumab), alemtuzumab, daclizumab, mitoxantrone or hematopoietic stem-cell transplant
- Female who are pregnant, nursing or unwilling to use contraception up to six months after the second course of the infusion (or 12 months after the first infusion)
- Treatment with steroids in the past 30 days
- Clinically unstable medical or psychiatric disorders at the time of screening that require acute treatment as determined by the PI

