#### Intervention

##### Investigational treatments

The intervention in this study is the two courses of infusions of ocrelizumab, an FDA approved medication for relapsing MS. The patients will receive ocrelizumab 300 mg IV infusion on days one and 15, according to the standard infusion protocols. The protocols include pre-medicating with acetaminophen 650 mg orally, diphenhydramine 50 mg orally and methylprednisolone 125 mg IV. The anti-CD20 antibody infusion will be repeated in six months (single infusion of ocrelizumab 600 mg). These infusions are standard of care and are done according to the medication label. However, the infusions will not be repeated after these two courses of infusion (the first two infusion of 300 mg ocrelizumab two weeks apart is considered one course and the infusion of 600 mg of ocrelizumab six months later is considered the second course).

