## Statistical analysis

We will describe the demographic, clinical characteristics and MRI data of all participants before treatment with the B-cell depleting agent. We will report the proportion of participants who experience the primary endpoint of the study (return of the disease activity) and the time to failure event, using a Kaplan-Meyer curve. Proportion of patients with clinical relapse, new MRI activity or disability progression will separately be reported. Quality of life data will be analyzed using linear mixed effect models.

To look at the association between long-term response to B-cell depletion therapy and autoreactivity of B-cells at different stages of development, we will use logistic regression and Cox proportional hazards models with failure or time-to-failure event as the outcome variable and the above-mentioned proportion of auto-reactive B-cells at different stages of development and the change in proportions before and after treatment as the predictor variables. Failure event as defined in the Aim 1 is the return of disease activity after the third month post-first-infusion, objectively demonstrated by development of new T2 hyperintense lesions or Gd-enhancing lesions on the MRI or a clinical relapse that is confirmed with an objective change in the neurological examination or a corresponding new or enhancing lesion on the MRI that is obtained after the onset of symptoms.

Version: 2.0

Date: 3/8/2019

Using paired t-test, we will compare the frequency of autoreactive mature naïve B-cells, Treg and Tfh cells and cytokine production before treatment with ocrelizumab and after the B-cell repopulation.

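### Some pre-treatment immune samples may be drawn on interferon or glatiramer, so the pooled paired change mixes stopping that drug with the effect of ocrelizumab, chiefly for the Treg, Tfh, cytokine and phenotype measures

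*Combined protocol and SAP*

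**What the plan says.** **First sample.** The section on T and B-cell phenotypes and function has blood drawn "before start of the treatment with ocrelizumab (at the screening visit"). The schedule of events agrees.

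**Drugs allowed at that draw.** The inclusion criteria, in the synopsis and in the main text, admit patients who are "Naïve to disease modifying therapies or using an injectable therapy (interferons or glatiramer acetate"). For four other drugs the rule is: "if history of receiving natalizumab, fingolimod, dimethyl fumarate and teriflunomide, no exposure for past three months". The exclusion criteria bar "Treatment with steroids in the past 30 days", and bar anyone who ever received a B-cell depleter or certain other agents. No section requires an injectable to be stopped before the draw, or says when it is stopped.

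**Second sample.** It is drawn "12 or 18 months after the second course of ocrelizumab infusion (month 18 or 24 of the study"). Under Investigational treatments, "the infusions will not be repeated after these two courses of infusion". Under Discontinuation of study intervention, starting another MS drug without breakthrough disease counts as discontinuing the intervention. The intended state at the second draw is therefore off treatment.

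**Analysis.** The Statistical analysis section applies a paired t-test to autoreactive mature naive B-cells and to "Treg and Tfh cells and cytokine production before treatment with ocrelizumab and after the B-cell repopulation". It has no term, stratum or sensitivity analysis for the drug in use at screening. The study is single-arm. The sections on phenotypes and on tolerance checkpoints attribute the change to ocrelizumab or B-cell depletion.

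**The concern.** For a participant on interferon or glatiramer at screening, the interval between samples contains two changes of exposure: ocrelizumab was given, and another immune-acting drug was (by intention) no longer in use. The within-person difference cannot separate them. With no control arm, that difference is the only evidence on the mechanistic question.

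A change in Treg function, Tfh frequency or cytokine production could then be inflated or hidden by the earlier drug and still be reported as the effect of B-cell depletion. Participants who are treatment-naive at the draw are free of this problem, so the damage depends on how the 10 divide, which eligibility leaves open.

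**Working it through.** **Plan's own figure.** The Sample size section claims more than 90% power with 10 before and 10 after, two-sided α 0.05, for a fall from 48.9 ± 3.06% to 20.1 ± 0.9% in autoreactive mature naive B-cells.
- Difference: 48.9 − 20.1 = 28.8 points.
- If ± is an SD: pooled SD = √((3.06² + 0.9²)/2) = 2.26, and power is about 100%.
- If ± is a standard error from an assumed source sample of 10, 20 or 30: pooled SD 7.1, 10.1 or 12.4, and two-sample power above 99.9%, above 99.9% and 99.8%.
- Power stays at 90% or more up to a pooled SD of about 18.8.

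The claim reproduces. The issue is bias, not power.

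**Bias.** Let k be the number of the 10 on an injectable at the first draw, and b the shift in their first value due to that drug, assumed gone by the second draw. Bias in the mean fall = (k/10) × b. The documents give neither k nor b, so both are assumptions:
- k = 2, b = ±5: ±1 point.
- k = 5, b = ±10: ±5 points; a true fall of 28.8 would appear as 23.8 or 33.8.
- k = 10, b = ±10: ±10 points.

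**Could this create the assumed B-cell fall?** With k = 5, b would have to be 28.8 / 0.5 = 57.6 points, more than the whole assumed starting value of 48.9. With k = 10 it would still have to be 28.8 points. A modest drug effect cannot do this.

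**Measures with no stated expected change.** Suppose ocrelizumab has no effect. The chance that the paired t-test (n = 10, two-sided 5%) is significant, from 100,000 simulated trials per cell, is:

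| k | b | SD of differences 3.19 | 10.1 | 14.3 |
|---|---|---|---|---|
| 3 | 5 | 13.9% | 6.3% | 5.7% |
| 3 | 10 | 19.0% | 9.7% | 7.6% |
| 5 | 5 | 37.4% | 9.9% | 7.4% |
| 5 | 10 | 70.2% | 21.6% | 14.0% |
| 10 | 10 | 100% | 79.3% | 50.5% |

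The three SDs come from the B-cell figures with uncorrelated pairs: ± read as an SD, or as a standard error with source n of 10 or 20. The result depends only on k and the ratio b/SD, so it carries over to markers in other units. For b = 10 the ratios are 10/3.19 = 3.1, 10/10.1 = 1.0 and 10/14.3 = 0.7.

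**How much could an unexposed subset show?** Paired power for a true 28.8-point fall, at SDs of differences 10.1, 14.3 and 17.5 (source n of 30):
- 5 participants: above 99%, 91% and 78%.
- 3 participants: 71%, 48% and 36%.

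**Route into the response models.** The logistic and Cox models use the proportions of autoreactive B-cells and their change. Treg, Tfh and cytokine values are not listed as predictors, so any distortion reaches the models only if the injectable shifts autoreactive B-cell frequency.

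**The case against.** The strongest reply is that this is a declared pilot with an argued single-arm design, and that nothing in the documents shows interferon or glatiramer moving these markers. The Introduction's remark on prolonged immunosuppressive therapy concerns infections and cancers, not Treg or cytokine assays. The large false-positive rates need large assumed shifts; with k = 3, b = 5 and SD 10.1 the rate is 6.3%, close to nominal. Treatment history is already taken at screening. A subset of three to five participants settles little, and may be empty.

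Most of this stands as a limit on size. It does not remove the mixing: no section separates the two exposures, and the plan states its attribution without qualification.

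A reader might also infer that the plan ignores recent disease-modifying drugs altogether. It does not. The four listed drugs carry a three-month no-exposure rule, longer than the steroid window, and several agents are excluded outright. Only the injectables have no interval, and drugs under the three-month rule are a lesser concern. Nor do the documents say that the steroid exclusion exists to protect the immune sample.

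**Conclusion.** The point holds in a limited form. For participants on an injectable at screening, the pooled paired change cannot be credited to ocrelizumab alone. This matters most for Treg, Tfh, cytokine and other phenotype measures, and less for autoreactive mature naive B-cells.

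The documents give neither the number affected (0 to 10) nor the size or direction of the shift; the ±1 to ±10 point range is illustrative. It rests on the injectable being out of use by the second draw. The documents imply this but do not state it, and participants who restart treatment under the treatment stop rules would not be drug-free then.

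Three stronger readings are not supported:
- That a finding of corrected B-cell tolerance would be an artefact of drug withdrawal. The assumed fall is too large for a modest shift to produce.
- That distorted Treg, Tfh or cytokine changes feed the response models. Those variables are not among the predictors.
- That a treatment-naive comparison would establish attribution. It remains an uncontrolled before/after contrast in patients selected for at least two enhancing lesions.

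**What to change.** In the Statistical analysis section:
- Use the screening treatment history to classify each participant by disease-modifying drug and date of last exposure at the first draw.
- Show all individual before/after pairs for each marker, flagged by that status.
- Add a sensitivity paired comparison in participants not on a disease-modifying drug at the draw, with the treatment-naive shown separately, labelled descriptive.
- Report the pooled result as a before/after change. Where the pattern is confined to participants who were on an injectable, do not attribute it to ocrelizumab alone.

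This needs no new visit, blood draw or change of eligibility. The history is already needed to verify eligibility, though the last-exposure date should be an explicit data field. The cost is one small, imprecise extra comparison. Specify it before the immune results are known.

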#### [Analysis of the central and peripheral B-cell tolerance checkpoints](#)

Single CD19+CD10hiCD21-/loIgMhiCD27 new emigrant/transitional and CD19+CD10+CD21+IgM+CD27 mature naïve B-cells will be isolated from the blood of these patients before and after treatment and frequencies of polyreactive, HEp-2 reactive and anti-nuclear clones will be determined as previously described. In brief, Ig heavy and light chain genes will be amplified by RT-PCR and 20-30 immunoglobulin genes from single new emigrant/transitional and mature naïve B-cells will be cloned and expressed in vitro. Recombinant antibodies will be tested for HEp-2 reactivity and polyreactivity by ELISAs and anti-nuclear reactivity using indirect fluorescence assay on HEp-2 slides as previously described. Recombinant antibodies will be considered polyreactive when they recognized all three antigens tested individually (dsDNA, insulin, and LPS) using supernatants tested at 1 $\mu$ g/ml antibody concentrations and three 1:4 dilutions in PBS as reported. In HEp-2 and polyreactivity ELISAs, ED38 recombinant antibody will be used as positive control. Hence, we will determine if B-cell depletion can correct the impaired removal of developing autoreactive B-cells in the periphery of people with MS and is associated with disease suppression.

**Safety and adverse effect monitoring:** Potential participants will have lab work done (liver function tests, complete blood count, Hepatitis- B surface antigen, Hepatitis-B core antibody, HIV antibody, lymphocyte subset including CD19+ B-cells, total IgG and IgM and urine pregnancy test) as part of routine clinical care to assess for study eligibility and as the baseline for future comparison. Patients who are positive for Hepatitis-B surface antigen (HBsAg) or Hepatitis-B core antibody (HBcAb) will be excluded from participation.

Ocrelizumab has been extensively used in people with MS. In this small study, with limited and short-term use of B-cell depleting antibodies, we do not expect to see unanticipated side effects worth reporting, however, the most important safety consideration in this setting is the return of disease activity after B-cell reconstitution. Unlike patients who stop medications such as natalizumab and fingolimod and may experience severe return of the disease activity, rebound phenomenon has never been described in association with cell depleting antibodies such as alemtuzumab, rituximab or ocrelizumab. For example, most patients who receive alemtuzumab have severe MS, uncontrolled with other DMTs. Most patients only receive two courses of treatment with alemtuzumab and after lymphocyte reconstitution, there has been no reports of severe return of disease activity (rebound). Similar to this situation, we do not anticipate that patients with B-cell reconstitution after B-cell depletion therapy will experience rebound. Although a subgroup of patients may have return of disease activity, the disease activity will be mild and non-disabling.

Version: 2.0

Date: 3/8/2019

To comply with rules and regulations of performing clinical studies, we will record all safety data during the study. Upon signing the informed consent form, each participant will be given the names and telephone numbers of study staff for reporting adverse events and medical emergencies.

**Adverse event (AE):** An AE is the development or worsening of any undesirable symptom, sign or medical condition occurring after starting the study drug even if the event is not considered related to study medication. Medical conditions or diseases present before starting study drug are only considered AEs if they worsen after initiating study medication. At each study encounter, the occurrence of AEs should be sought by non-directive and directive questioning. AEs may also be collected when they are volunteered by the subjects during or between encounters.

**Serious adverse event (SAE):** An SAE is defined as an event which:

- is fatal or life-threatening
- results in persistent or significant disability
- constitutes a birth defect/congenital abnormality
- requires inpatient hospitalization for at least 24 hours or prolongation of existing hospitalization for at least 24 hours
- is medically significant

**Data safety monitoring committee (DSMB):** DSMB is not required for a small study using a medication that is FDA-approved for the condition, however, we will have the following treatment stop and study termination rules:

**Treatment stop rules:** Stopping the study is equivalent to restarting the B-cell depleting antibody (i.e. ocrelizumab) or another DMT, if there is medical contraindication to the continued use of ocrelizumab (e.g. development of allergic or severe infusion reactions during the last infusion). The followings are the criteria for restarting the DMT (stopping the study).

1. A clinical relapse, affecting optic nerves (with worst visual acuity of 20/50 or less) or causing motor weakness, ataxia, bladder or bowel symptoms. Pseudo-relapses are not uncommon among patients with MS. When in doubt, the PI will use MRI (similar to the standard of care) to confirm development of new lesions corresponding to patient's symptoms (based on the possible localization of the symptoms).
2. Development of two new T2 hyperintense lesions or two gadolinium enhancing lesions on any MRI after the baseline MRI. The baseline MRI was defined the MRI that is obtained three months after the first ocrelizumab infusion.

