## Known Potential Risks

By limiting the participants to two courses of treatment with ocrelizumab, participants are at higher risk of return of MRI or clinical disease activity. However, it is well within the standard practice to start patients with safer, but less efficacious disease modifying treatments and if the disease activity continued, to escalate to higher efficacy medications. Even in the case of more effective medications such as alemtuzumab, the standard practice is treatment with only two courses of the medication and retreatment if the disease activity returns. In this study, we will restart the treatment with ocrelizumab in patients who experience the return of the disease activity, a practice similar to escalation or retreatment which are standards of care.

Loss of privacy is another risk of participating in this study. Several mechanisms will help prevent loss of privacy. Access to the data will be limited to study personnel and the database will be password-protected. Furthermore, each member of the study team will be limited to only the data they need to perform their tasks so that privacy is protected as much as possible. Only study personnel who need to access the database will be given such access.

The risks associated with the study are minimal, and an adequate protection plan is in place; as such, the potential benefits exceed the potential risks. The participation of patients is completely voluntary; the alternative to the patients is to not participate in the study. Lack of participation will in no way compromise the relationship they have with their neurologists or the ongoing care they receive for their MS.

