## Study intervention discontinuation and participant discontinuation/withdrawal

### Discontinuation of study intervention

The study intervention is treatment with two courses of ocrelizumab. So, discontinuation from study intervention equates to not completing two courses of treatment with ocrelizumab or restarting the ocrelizumab or starting another MS disease modifying treatment after two courses of treatment with ocrelizumab for reasons other than breakthrough disease activity. All patients started on treatment will be followed in the study. Participants are free to withdraw from participation in the study at any time upon request. If a participant is unable to obtain insurance authorization for ocrelizumab within 90 days of screening visit (absent an administrative delay or other reason that is expected to be easily resolvable), the participant will be deemed a screen failure and will be replaced.

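### The plan contradicts itself on follow-up after a DMT restart, and one reading would understate confirmed disability among those who restart

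*Combined protocol and SAP*

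**What the plan says.** The paragraph on the data safety monitoring committee explains that none is required and adds that "we will have the following treatment stop and study termination rules". Treatment stop rules then states: "Stopping the study is equivalent to restarting the B-cell depleting antibody", or starting another DMT where ocrelizumab is contraindicated. It repeats the equation when it introduces the criteria: "The followings are the criteria for restarting the DMT (stopping the study". There are two criteria. The first is "A clinical relapse, affecting optic nerves (with worst visual acuity of 20/50 or less) or causing motor weakness, ataxia, bladder or bowel symptoms". The second rests on MRI alone: two new T2 lesions or two enhancing lesions on any scan after the month 3 baseline.

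Other sections point the other way:

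- **Discontinuation of study intervention** says "All patients started on treatment will be followed in the study". It counts a later DMT as discontinuation of the intervention only in some cases, for example "starting another MS disease modifying treatment after two courses of treatment with ocrelizumab for reasons other than breakthrough disease activity".
- **Known Potential Risks** says "In this study, we will restart the treatment with ocrelizumab in patients who experience the return of the disease activity".

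Under Secondary outcome, a one-step EDSS change counts only if it is "confirmed on a clinical visit six months later". Statistical analysis reports the proportion with disability progression and analyses quality of life with linear mixed models. It gives no rule for participants who restart. End of Study Definition ties completion to the last visit or procedure and does not mention restart.

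**The concern.** A six-month confirmed outcome needs a visit six months after the change is first seen. If restart takes a participant out of the study, worsening that begins at the triggering event cannot be confirmed in study data, however long it lasts. The loss would be informative, because the first restart criterion names relapse types likely to move the EDSS.

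The section on safety monitoring treats return of disease activity as the leading safety question and expects any return to be mild and to leave no disability. It also lists persistent disability among the serious adverse event criteria. Whether a deficit persists can be judged only by observing the participant after the event. If restart ends data collection, the plan loses that information for those who restart, along with their later Neuro-QoL and safety records.

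**Working it through.** The plan states no figure on this point, so there is nothing to reproduce. The check compares sections and then gives an illustration.

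**1. Does any section settle the status of participants who restart for breakthrough activity?**

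| Section | What it implies |
|---|---|
| Treatment stop rules | Restart is equated with stopping the study, twice |
| Discontinuation of study intervention | All treated patients are followed, but restart for breakthrough activity is left out of the definition of discontinuation |
| Known Potential Risks | Restart happens within the study |
| End of Study Definition | Silent on restart |
| Statistical analysis | Silent on restart, on unconfirmed worsening and on the denominator |

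None does.

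**2. What follows under each reading?**

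- *Restart ends follow-up.* Worsening that starts at the triggering event has no confirming study visit and cannot count. Confirmed improvement is lost in the same way. Worsening already confirmed before restart still counts.
- *Everyone treated is followed.* The confirming visits are kept. EDSS after restart then reflects retreatment and needs to be labelled so.

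**3. Who is affected?** The primary failure event sets no minimum lesion count and includes any qualifying relapse. The listed restart criteria are narrower. A participant with one new lesion, or with a purely sensory relapse, fails without meeting either criterion. Conversely, a participant who restarts on the MRI criterion may have no worsening to confirm. The broader statement in Known Potential Risks would extend restart to anyone with returning activity, so who restarts is itself stated in two ways.

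**4. Primary endpoint.** A triggering event that meets the primary definition is already recorded as a failure with its time. Ending follow-up afterwards changes the Kaplan-Meier curve little.

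**5. Size (illustration).** The planned number is N = 10, so one unconfirmed case is 1/10 = 10 percentage points. The following inputs are assumptions, because the documents give no rates:

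- k participants restart (2, 3 or 5);
- a share q of them (20% or 50%) has worsening that begins at the trigger and would be confirmed at six months;
- a share p0 = 10% of the others has confirmed worsening.

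Follow-up kept: [k × q + (10 − k) × p0] / 10. Follow-up ended, denominator 10: (10 − k) × p0 / 10.

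| k | q | Follow-up kept | Follow-up ended |
|---|---|---|---|
| 2 | 20% | (0.4 + 0.8)/10 = 12% | 0.8/10 = 8% |
| 2 | 50% | (1.0 + 0.8)/10 = 18% | 8% |
| 3 | 20% | (0.6 + 0.7)/10 = 13% | 0.7/10 = 7% |
| 3 | 50% | (1.5 + 0.7)/10 = 22% | 7% |
| 5 | 20% | (1.0 + 0.5)/10 = 15% | 0.5/10 = 5% |
| 5 | 50% | (2.5 + 0.5)/10 = 30% | 5% |

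If the denominator is restricted to participants who did not restart, the reported figure is p0 = 10% throughout.

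**The case against.** The strongest reply is that the stop rules only use a loose label. They say nothing about cancelling visits, withdrawing the participant or closing data collection. The section that governs discontinuation says that treated patients are followed. Together with the section on loss to follow-up, it names only two exits after treatment starts: withdrawal on request and loss to follow-up. Most visits are described as standard of care, so EDSS would probably still be measured in clinic after a restart. Severity at the event is captured in any case, because a relapse requires a measured EDSS change or a corresponding lesion, and relapses and MRI activity are reported separately. The affected outcome is a descriptive secondary proportion in a 10-patient pilot.

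Much of this stands. It makes the harm conditional and limits it to persistence after restart. It does not remove the contradiction. The same text also speaks of study termination, restart for breakthrough activity is left out of the discontinuation definition, and no section says that clinic EDSS values recorded after restart enter the study data.

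A reader might also infer that worsening first seen at month 30 is a further instance, because the schedule shows no later visit. That does not follow from this contradiction. A change first seen at the last visit is unconfirmable in any study of fixed length, and the planned length is itself unclear:

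- the schedule ends at month 30;
- Study design runs to 2.5 years after the baseline MRI (3 + 30 = month 33);
- the Synopsis runs to at least 2.5 years after the last dose (6 + 30 = month 36, with the second course at month 6).

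**Conclusion.** The contradiction is real and should be resolved. If the stop rules govern as worded, the confirmed-disability proportion could be understated among participants who restart, and their later Neuro-QoL and safety data would be missing. If the statement that all treated patients are followed governs, nothing is lost except the clarity of post-restart EDSS.

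The only firm size is 10 percentage points per unconfirmed participant. Under the assumed inputs, the expected proportion is 12% to 30% with continued follow-up and 5% to 8% without it (denominator 10). Those ranges illustrate the mechanism and are not forecasts.

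Three stronger readings are tempting, and the documents do not support them:

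- *Restart definitely ends follow-up.* The sections conflict, and several favour continued follow-up.
- *Every participant who fails is lost.* The listed restart criteria are narrower than the failure event, and one of them is MRI-only.
- *The primary endpoint is compromised.* The failure is normally recorded before or at restart.

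**What to change.** Reconcile Known Potential Risks, Discontinuation of study intervention and Treatment stop rules, and state that:

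1. restarting a DMT ends the drug-free observation period but not study participation or data collection;
2. the EDSS, Neuro-QoL and safety assessments already scheduled continue after restart to the end of planned follow-up, with that length stated consistently in the Synopsis, Study design and Schedule of events;
3. confirmed disability is reported for all treated participants, with post-restart data flagged;
4. worsening without a confirming visit is listed separately, and the denominator is stated.

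The cost is mainly wording. Schedule of events describes everything except consent, PBMC collection and Neuro-QoL as routine care, so the added burden is a few Neuro-QoL administrations and some data entry. One limitation remains: EDSS after restart reflects retreatment as well as the relapse, which is why those data need a flag. The differing statements on who restarts must also be reconciled. This point takes no view on which is right and proposes no change to the restart criteria or to treatment.
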